6.2. Statistical Considerations for Secondary Objectives

- 6.2.1. To examine the safety of axitinib, we will tabulate reported adverse events (adverse events will be recorded per CTCAE v4.0).
- 6.2.2. To examine the tolerability of axitinib, we will use the FKSI-15 (Functional Assessment of Cancer Therapy-Kidney Specific Index-15, Appendix E) questionnaire and compare changes in response between different time points.
- 6.2.3. We will evaluate disease-free survival by plotting Kaplan-Meier curves and estimating median recurrence-free survival. Time to death or recurrence will be defined as the time from treatment start until death, recurrence or progressive disease, whichever comes first. Patients who did not die, recur or have progressive disease will be censored at date of last follow-up. These will be compared to contemporary, matched (2:1 matching, for age group, stage and grade), historical controls. Although small differences in recurrence-free and overall survival might not be detected in this current trial, this information will help us when designing future large trials with this particular agent.

7. Treatment Plan (Table 4)

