7.2. Treatment Phase

7.2.1. Eligible patients will provide written informed consent.

7.2.2. Prior to the initiation of therapy, a surgical date will be established.

7.2.3. Treatment Assignment: Each patient will receive a total of 12 weeks of axitinib. Patients will take the last dose of axitinib 1.5 days prior to surgery.

7.2.4. Adverse events monitoring and reporting:

7.2.4.1. Adverse events:

7.2.4.1.1. The investigator is responsible for determining the attribution of adverse events to study drug.

7.2.4.1.2. Adverse events will be documented in the medical record and entered into the case report form according to the Recommended Adverse Event Recording Guidelines for Phase II protocol (see table below).

Recommended Adverse Event Recording Guidelines					
Attribution	Grade 1	Grade 2	Grade 3	Grade 4	Grade 5
Unrelated	Phase I	Phase I	Phase I Phase II	Phase I Phase II Phase III	Phase I Phase II Phase III
Unlikely	Phase I	Phase I	Phase I Phase II	Phase I Phase II Phase III	Phase I Phase II Phase III
Possible	Phase I Phase II	Phase I Phase II Phase III	Phase I Phase II Phase III	Phase I Phase II Phase III	Phase I Phase II Phase III
Probable	Phase I Phase II	Phase I Phase II Phase III	Phase I Phase II Phase III	Phase I Phase II Phase III	Phase I Phase II Phase III
Definitive	Phase I Phase II	Phase I Phase II Phase III	Phase I Phase II Phase III	Phase I Phase II Phase III	Phase I Phase II Phase III

7.2.4.1.3. Adverse events will be assessed at each patient visit, documented in the medical record, and entered into the CRFs. Adverse events should be treated appropriately. Such treatment may include changes in axitinib treatment including possible interruption or discontinuation, starting or stopping concomitant treatments, changes in the frequency or nature of assessments, hospitalization, or any other medically required intervention. Once an adverse event is detected, it should be followed until its resolution, and assessment should be made at

each visit of any changes in severity, the suspected relationship to the axitinib, the interventions required to treat it, and the outcome. In addition, Pfizer requires reporting of serious adverse events on the M.D. Anderson SAE forms. Reporting of adverse events will be done according to NCI Common Terminology Criteria for Adverse Events (CTCAE) version 4.0. The following items will be recorded at least:

- Event description
- Date of onset of AE
- CTCAE grade/severity (1,2,3,4,5)

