- Relationship to treatment with axitinib (unrelated, unlikely, possible, probable, highly probable/definite)
- Action taken (none, temporarily discontinued agent, drug treatment given/specify, permanently discontinued agent, non-drug treatment given/specify, hospitalization)
- Date of AE stop
- Outcome (recovered without sequelae, recovered with sequelae, ongoing, worsened, death)
- Serious AE (yes, no)

7.2.4.2. Serious Adverse events (SAE):

7.2.4.2.1. SAE reporting-SAEs will be recorded on a SAE form (Appendices G and H), in addition to the CRF AE documents. SAEs will be reported within 24 hours to Pfizer (Please see Pfizer SAE reporting guidelines in the appendix section)

7.2.4.2.2. SERIOUS ADVERSE EVENT REPORTING – M. D. Anderson Cancer Center: The following SAE Reporting Requirements, since this is an MDACC sponsored IND study, and all SAEs must be reported to IND Sponsor representative – the IND Office - according to the following:

7.2.4.2.2.1. A serious adverse event is – any adverse drug experience occurring at any dose that results in any of the following outcomes:

- Death
- A life-threatening adverse drug experience – any adverse experience that places the patient, in the view of the initial reporter, at immediate risk of death from the adverse experience as it occurred. It does not include an adverse

experience that, had it occurred in a more severe form, might have caused death

- Inpatient hospitalization or prolongation of existing hospitalization
- A persistent or significant disability/incapacity – a substantial disruption of a person’s ability to conduct normal life functions
- A congenital anomaly/birth defect

7.2.4.2.2.2. In this protocol, we will not report those hospitalizations resulting from routine treatment not associated with any deterioration in condition, treatment for a pre-existing condition that is unrelated to axitinib and has not worsened since the start of axitinib; or for treatment on an emergency outpatient basis for an event not fulfilling any of the definitions of a SAE given above and not resulting in hospital admission.

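### The protocol gives unreconciled rules for which adverse events enter the CRF; if the Phase II table governs, the safety tabulation omits Grade 1-2 events judged unrelated or unlikely

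*Combined protocol and SAP*

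**What the plan says.** Section 7.2.4.1.2 has events charted and then "entered into the case report form according to the Recommended Adverse Event Recording Guidelines for Phase II protocol". The table's first two rows begin "Unrelated Phase I Phase I Phase I Phase II" and "Unlikely Phase I Phase I Phase I Phase II", so for these attributions Phase II entry starts at Grade 3. Attribution is decided on site: "The investigator is responsible for determining the attribution of adverse events to study drug" (7.2.4.1.1).

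Section 7.2.4.1.3 then states: "Adverse events will be assessed at each patient visit, documented in the medical record, and entered into the CRFs". It names no limit by grade or attribution. Its minimum list of data items includes "CTCAE grade/severity (1,2,3,4,5" and "Relationship to treatment with axitinib (unrelated, unlikely, possible, probable, highly probable/definite".

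Sections 7.2.10 (weeks 3, 7 and 12) and 7.3.2 (week 19) also have adverse events recorded in the chart and the relevant CRFs, again without a limit. Section 7.2.4.2.1 puts SAEs on a separate form on top of the CRF adverse-event pages, and 7.2.4.2.2.3 has SAEs reported to the IND office whatever their attribution.

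The analysis in 6.2.1 is one sentence: "we will tabulate reported adverse events", graded by CTCAE v4.0. It does not say whether the table is all-cause or treatment-related.

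**The concern.** Safety is part of the first secondary objective (4.2.1), and its adverse-event analysis is a tabulation of whatever was reported. The recording rule therefore fixes the numerator, and the protocol does not state that rule consistently.

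Attribution matters more here than in a randomised trial. There is one treated group, and the historical controls in 6.2.3 are named only for disease-free survival. Nothing in the data can check whether low-grade fatigue or nausea called unrelated really was unrelated. If that judgment is applied before data entry, it also decides whether the event exists in the study database. An analyst working from the CRFs could not produce an all-cause, any-grade table, nor see how often the filter had acted.

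**Working it through.** The plan states no adverse-event rate, so there is no figure to reproduce. The check has three parts.

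**1. Read the guideline table for Phase II (7.2.4.1.2).**

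| Attribution | G1 | G2 | G3 | G4 | G5 |
|---|---|---|---|---|---|
| Unrelated | no | no | yes | yes | yes |
| Unlikely | no | no | yes | yes | yes |
| Possible | yes | yes | yes | yes | yes |
| Probable | yes | yes | yes | yes | yes |
| Definitive | yes | yes | yes | yes | yes |

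Four of 5 × 5 = 25 cells are omitted, so 25 − 4 = 21 reach the CRF. All Grade 3-5 cells are covered, as are all cells at possible or above.

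**2. Set the sections side by side for two events.**

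- *Grade 1 nausea at week 7, judged unlikely.* By the table it stays out of the CRF. By 7.2.4.1.3 and 7.2.10 as written, it goes in.
- *Grade 2 event judged unrelated that leads to hospital admission, outside the exclusions in 7.2.4.2.2.2.* Seriousness is defined by outcome, not grade, so this is an SAE. It goes on the SAE form and, by 7.2.4.2.1, is expected in the CRF as well. The table leaves it out.

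No section says which rule prevails. The top attribution level is also named differently in the table and in the data-item list, which suggests that the two were not harmonised.

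**3. Direction and size if the table governs.** The filter removes events and never adds any, so all-cause rates for Grades 1-2 taken together, and for any grade, can only fall or stay the same.

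For size, let p be the true share of the 24 patients who have a given term at Grade 1-2 only. Let q be the share of those patients in whom every occurrence is judged unrelated or unlikely. Then

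recorded rate = p × (1 − q).

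The documents give neither p nor q. The values below are assumptions, for illustration only.

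| p (expected patients of 24) | q = 0 | q = 10% | q = 25% | q = 50% |
|---|---|---|---|---|
| 20% (4.8) | 20% | 18% (4.3) | 15% (3.6) | 10% (2.4) |
| 40% (9.6) | 40% | 36% (8.6) | 30% (7.2) | 20% (4.8) |
| 60% (14.4) | 60% | 54% (13.0) | 45% (10.8) | 30% (7.2) |

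For example, 0.40 × (1 − 0.25) = 0.30, and 24 × 0.30 = 7.2 patients. At q = 0 nothing is lost.

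**The case against.** The best reply is that there is no contradiction. Section 7.2.4.1.3 never says that *all* events are entered. It follows directly after a specific Phase II rule and can be read as covering timing, follow-up and data fields for the events that the rule selects. Where the authors meant an obligation regardless of attribution, as for SAEs, they said so. The five attribution levels and five grades are needed under the table too, since unrelated events are entered from Grade 3 and Grade 1-2 events from possible upward. This stands: a reader might infer that 7.2.4.1.3 orders entry of every event, but the text does not go that far. It is silent on the filter, and so are 7.2.10 and 7.3.2. That reading also leaves the SAE conflict unresolved.

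Three other stronger inferences fail:

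- *The omitted events are lost for good.* Both paragraphs keep adverse events in the medical record, so chart review could recover them.
- *The required reassessment of relationship at each visit becomes impossible.* The text does not require this to be done in the CRF. An event later judged possible, or worsening to Grade 3, would move into a Phase II cell.
- *The understatement has a known size.* It does not. A share of events cannot be applied directly to patients either, because one occurrence judged possible or reaching Grade 3 keeps the patient in the count. Fatigue, nausea and anorexia are listed as common axitinib effects in 2.1.3, which makes a judgment of possible or higher more likely for them.

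It is also fair to say that no trial decision turns on these events, that FKSI-15 measures tolerability without an attribution filter (6.2.2), and that a phase-specific recording guideline is an open design choice. These points limit the importance. They do not supply a defined numerator for 6.2.1.

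**Conclusion.** The point holds in a limited form. The sections on CRF entry are not reconciled, and for a low-grade SAE judged unrelated or unlikely they conflict. If the table governs, the single-arm safety table depends on prior investigator attribution, and its all-cause Grade 1-2 and any-grade rates are biased downward or, at best, unbiased. If the unrestricted wording governs, there is no such bias.

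The size is unknown. It depends on how often low-grade events are called unrelated or unlikely, which the documents do not give. Grade 3-5 rates and events judged possible or above are captured either way. The dose rules (7.2.6) work on axitinib-related events, and the stopping rules and primary endpoint (6.1) on response, progression, treatment-related deaths and surgical outcomes, so none of them is affected. This is a worthwhile, inexpensive improvement to a secondary analysis and no threat to the trial's main conclusion.

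**What to change.** In 7.2.4.1.2, state one CRF rule: adverse events of any grade and any attribution are entered, with attribution kept as a data field. Use one set of attribution labels throughout. In 6.2.1, specify an all-cause table by maximum grade, and a second table restricted to axitinib-related events.

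The events are already assessed and charted at each visit, so the cost is a wording change and modest extra data entry for 24 patients. The price in presentation is that all-grade rates may look slightly less favourable.

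If the sponsor prefers to keep the filter, then 7.2.4.1.3, 7.2.10 and 7.3.2 should cross-refer to it, SAEs should be exempt from it, and the safety table should be labelled as excluding Grade 1-2 events judged unrelated or unlikely. That removes the ambiguity but leaves the dependence on attribution.

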Grade 4 hematologic treatment-related toxicity**	Interrupt dosing; re-start at one lower dose level as soon as improvement to CTCAE Grade ≤ 2 occurs within 2 weeks. If a patient requires dose reduction below 2 mg BID when above fails, consideration should be given to stop axitinib if this recurs.
Grade 4 nonhematologic treatment-related toxicity	Stop Axitinib

* Patients who develop Grade 3 nonhematologic toxicities that are controlled with symptomatic medications or Grade 3 asymptomatic biochemistry laboratory abnormalities may be continued at the same dose level at the discretion of the investigator.

** Patients who develop Grade 4 lymphopenia or Grade 4 asymptomatic biochemistry laboratory abnormality may continue study treatment without interruption.

- 7.2.6.3. Axitinib dose-reduction for hypertension:
- 7.2.6.3.1. Electronic BP monitors will be provided to each patient for home use. Instructions to use them will be provided (Appendix F) and demonstration of their use will be done in the visit

prior to starting axitinib intake. Patients will self-monitor BP at home twice daily (before each axitinib dose). All BP measurements will be recorded in a diary (Appendix J) and brought to the clinic at each clinic visit. Patients will be instructed to inform their physicians in the event of systolic BP greater than 150 mmHg or diastolic BP greater than 100 mmHg, or if they develop symptoms related to elevated BP (e.g. headache or visual disturbance). During normal business hours the patient will call the urology research nurse for instructions. Outside of normal business hours, the patient will call the urologist on call through the page operator, and inform the urologist that they are enrolled in the axitinib trial. The urologist on call will then contact one of the axitinib study members ([name], [name], [name] or [name]) for further instructions. Written contact information will be provided to each patient prior to initiation of axitinib (Appendix I)

- 7.2.6.3.2. New or additional antihypertensive therapy should be started if 2 BP readings, preferably taken in the clinic and separated by at least 1 hour, show the following: 2 systolic BP readings greater than 150 or 2 diastolic BP readings greater than 100 mm Hg. Alternately, the dose of existing antihypertensive medication(s) may be increased. If the patient is already on maximal antihypertensive treatment, the axitinib dose should be reduced by 1 dose level.

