- 7.2.6.3.3. Patients who have 2 systolic BP readings, separated by at least 1 hour, greater than 160 mm Hg, or 2 diastolic BP readings, separated by at least 1 hour, greater than 105 mm Hg, should have treatment with axitinib held. (Note: if axitinib is held, patients receiving antihypertensive medications should monitor closely for hypotension and restart axitinib at one lower dose level as soon as BP is <150/100 mm Hg. Plasma half-life of axitinib is 2 – 6 hours and BP usually decreases within 1-2 days following dose interruption.) Treatment with axitinib should be restarted at 1 lower dose level as soon as the systolic blood pressure reduces to less than 150 mm Hg and the diastolic BP reduces to less than 100 mm Hg.
- 7.2.6.3.4. Patients who develop recurrent systolic hypertension (2 BP readings separated by at least 1 hour show systolic pressure >150 mm Hg) or recurrent diastolic BP >100 mm Hg following previous axitinib dose reduction should undergo another dose reduction by one dose level.
- 7.2.6.3.5. Patients removed from treatment for intolerable toxicity should still be followed with regular tumor assessments (every 4 months for 1 year, every 6 months for the next 2 years and every 12 months for one more year) until disease progression or start of new treatment, and for survival thereafter until study completion. Guidance on dose interruption and reduction for hypertension is summarized in the table below.

7.2.6.3.6. The antihypertensive medications (if the patient is taking any) will be tapered after axitinib is stopped, in order to maintain a blood pressure level that is less or equal to 140/90. Once the patient is at this blood pressure level, his blood pressure/blood pressure medications will be managed by his primary care physician.

HYPERTENSION MANAGEMENT PLAN FOR AXITINIB			
Degree of Blood Pressure Elevation			Management
Systolic Pressure	OR	Diastolic Pressure	
2 BP readings separated by at least 1 hour show systolic pressure >150 mm Hg		2 BP readings separated by at least 1 hour show diastolic pressure >100 mm Hg	If not on maximal antihypertensive treatment, institute new or additional antihypertensive medication and maintain dose of axitinib. If on maximal antihypertensive treatment, reduce axitinib to one lower dose level.

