2 BP readings separated by at least 1 hour show systolic pressure >160 mm Hg	OR	2 BP readings separated by at least 1 hour show diastolic pressure >105 mm Hg	Interrupt dosing*; adjust antihypertensive medication; as soon as BP is less than 150/100 mm Hg, restart axitinib at one lower dose level.
Recurrent hypertension following previous dose reduction (2 BP readings separated by at least 1 hour show systolic pressure >150 mm Hg)	OR	Recurrent diastolic BP >100 mm Hg (2 BP readings separated by at least 1 hour) following previous dose reduction	Repeat axitinib dose reduction by one lower dose level. If a patient requires dose reduction below 2 mg BID, interrupt dosing adjust antihypertensive medication; as soon as BP is less than 150/100 mm Hg, restart axitinib. Consideration should be given to stop axitinib if this recurs.

* If axitinib is held, patients receiving antihypertensive medications should monitor closely for hypotension. Plasma half-life of axitinib is 2 – 6 hours and BP usually decreases within 1-2 days following dose interruption.

7.2.6.4. Axitinib dose-reduction for proteinuria:

7.2.6.4.1. If urinalysis shows protein qualitative level \geq 100 (equivalent to \geq 2+ proteinuria on dipstick), perform 24-hour urine collection. Dosing may continue while waiting for test results. [Equivalence of protein qualitative levels on urine dipstick and urinalysis are as follows: 1+ on dipstick is equivalent to 30 on urinalysis, 2+ on dipstick is equivalent to 100 on urinalysis, 3+ on dipstick is equivalent to 300 on urinalysis, and 4+ on dipstick is equivalent to >2000 on urinalysis]

7.2.6.4.2. If < 2 g proteinuria/24 hour is reported, continue dosing at the same dose level.

7.2.6.4.3. If ≥ 2 g proteinuria/24 hours is reported, hold dosing and repeat 24 hour urine collection for proteinuria and creatinine clearance (interval at investigator discretion) until proteinuria is < 2 g/24 hours. Restart axitinib at the same dose or one lower dose level at discretion of the investigator.

7.2.6.4.4. Patients removed from treatment for intolerable toxicity should still be followed with regular tumor assessments (every 4 months for 1 year, every 6 months for the next 2 years and every 12 months for one more year) until disease progression or start of new treatment, and for survival thereafter until study completion.

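### The hypertension rules give two different doses for one group of previously reduced patients, and at 2 mg BID a restart instruction cannot be carried out

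*Combined protocol and SAP*

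**What the plan says.** Sections 7.2.6.3.2 to 7.2.6.3.4 correspond to the three rows of the Hypertension Management Plan table.

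- **Row 1.** The systolic trigger is "2 BP readings separated by at least 1 hour show systolic pressure >150 mm Hg"; the diastolic trigger is >100. The action depends on antihypertensive treatment: "If not on maximal antihypertensive treatment, institute new or additional antihypertensive medication and maintain dose of axitinib". Otherwise: "If on maximal antihypertensive treatment, reduce axitinib to one lower dose level". Section 7.2.6.3.2 has the second branch, "If the patient is already on maximal antihypertensive treatment, the axitinib dose should be reduced by 1 dose level", and calls for new or increased antihypertensives, but it does not say what happens to the axitinib dose when treatment is not maximal.
- **Row 2 and 7.2.6.3.3.** Above 160 systolic or 105 diastolic, axitinib is held. The table adds an adjustment of antihypertensives, then: "as soon as BP is less than 150/100 mm Hg, restart axitinib at one lower dose level".
- **Row 3 and 7.2.6.3.4.** The text covers "Patients who develop recurrent systolic hypertension (2 BP readings separated by at least 1 hour show systolic pressure >150 mm Hg", or a recurrent diastolic pressure above 100, after an earlier reduction, and orders another one-level reduction. The table says the same: "Repeat axitinib dose reduction by one lower dose level". Only the table has a floor clause: "If a patient requires dose reduction below 2 mg BID, interrupt dosing adjust antihypertensive medication". It then calls for a restart once pressure is below 150/100, at no named level, and for stopping to be considered if the problem recurs.

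The dose table in 7.2.5 runs 10, 7, 5 (start), 3 and 2 mg BID. Nothing lies below 2 mg BID.

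**The concern.** The row triggers overlap. Rows 1 and 2 are not limited to patients without an earlier reduction. Row 3 has no upper pressure limit and no condition on antihypertensive treatment. No sentence says which row governs when two apply.

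At stake is consistent dosing for the side effect that section 2.1.3 lists first, in a trial where patients measure their pressure twice daily and safety and tolerability are secondary objectives. Two clinicians following the protocol correctly could give different doses to patients with identical readings and background treatment. At the lowest dose level, a clinician following row 2 would have no level at which to restart.

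**Working it through.** The plan states no figure to reproduce here. The check applies each row literally to a patient with an earlier dose reduction, using the triggers and actions above and the dose levels in 7.2.5.

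| Two readings | Antihypertensives | Current dose (mg BID) | Row 1 | Row 2 | Row 3 |
|---|---|---|---|---|---|
| >150/100, not >160/105 | not maximal | 7, 5 or 3 | stay at 7, 5 or 3 | not triggered | go to 5, 3 or 2 |
| >150/100, not >160/105 | maximal | 7, 5 or 3 | go to 5, 3 or 2 | not triggered | go to 5, 3 or 2 |
| >160/105 | either | 7, 5 or 3 | lower band | hold, restart at 5, 3 or 2 | go to 5, 3 or 2; hold not mentioned |
| >150/100, not >160/105 | not maximal | 2 | stay at 2 | not triggered | interrupt; restart level not named |
| >150/100, not >160/105 | maximal | 2 | one level lower: none exists | not triggered | interrupt; restart level not named |
| >160/105 | either | 2 | lower band | hold; restart level does not exist | interrupt; restart level not named |

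**Line 1 is a contradiction.** Keeping the dose and lowering it cannot both be done. The size is one dose step: (7 − 5)/7 = 29%, (5 − 3)/5 = 40%, or (3 − 2)/3 = 33%.

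**The case can be reached.** A patient at 5 mg BID has two systolic readings of 165. Row 2 holds axitinib, adjusts antihypertensives without requiring the maximum, and restarts at 3 mg BID. Two later readings of 155, with treatment still not maximal, give 3 mg BID under row 1 and 2 mg BID under row 3. A patient whose only reduction came through row 1 was on maximal treatment at that time; if that is still so, line 2 applies and the rows agree.

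**Line 3 is not a dose conflict.** Holding under row 2 and restarting one level lower also delivers row 3's reduction. What is missing is only a restatement of the hold in row 3 and 7.2.6.3.4.

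**Line 6 cannot be carried out through row 2.** From the starting dose there are two reductions, 5 to 3 and 3 to 2, so a third event calling for a reduction falls at the floor. Row 2 and 7.2.6.3.3 then point to a level that is not in 7.2.5. Row 3 interrupts and restarts without naming a level. Section 7.2.6.3.4 has no floor clause and simply orders another reduction. Lines 4 and 5 show that row 1 also fails to match row 3 at this level.

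**An undefined term widens the overlap.** Neither row 3 nor 7.2.6.3.4 says whether the earlier reduction must have been made for hypertension. Section 7.2.6.2.6 reduces the dose for Grade 3 events, and 7.2.6.4.3 allows a restart one level lower after proteinuria.

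**The case against.** The best defence of line 1 is that row 3 is plainly the special case. It concerns recurrence after a reduction, and if row 1 still governed such patients, row 3's reduction would mostly repeat row 1's maximal-treatment branch. This is a sensible reading, but the protocol does not state it. The redundancy argument is also incomplete, because row 3 would still add the floor clause and the prompt to consider stopping. Row 1 remains unqualified.

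For the 2 mg BID case, the defence is that a patient there has normally had earlier reductions, so row 3's floor clause is available, and both rows interrupt. That stands in part. What remains is that row 2 does not refer to the clause and the clause names no restart level.

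Several stronger readings are tempting, and the documents do not support them.

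- *That the text as well as the table says to keep the dose.* Section 7.2.6.3.2 does not. Within the text alone, adding medication under 7.2.6.3.2 and reducing under 7.2.6.3.4 can both be followed. The clash is between row 1 on one side and row 3 with 7.2.6.3.4 on the other.
- *That the rows conflict whatever the background treatment.* Above 2 mg BID, rows 1 and 3 agree for patients on maximal antihypertensives.
- *That holding and reducing are opposite instructions above 160/105.* Above 2 mg BID they lead to the same next level, and 7.2.6.3.3 does not limit its hold to a first occurrence.
- *That sites would differ.* The protocol describes conduct at one institution, so any variation would be between a few treating physicians.
- *That the response rate would be distorted.* Dosing is individualised from 2 to 10 mg BID by design, and no frequency for the conflicting case can be drawn from the documents.

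**Conclusion.** The point holds in a narrow form. There is one direct contradiction: previously reduced patients above 150/100 but not above 160/105 who are not on maximal antihypertensives. It is worth one dose step, 29% to 40% depending on the current level above 2 mg BID. There is one instruction that cannot be carried out: row 2's restart at 2 mg BID, with no restart level in row 3 to fill the gap. The unrepeated hold above 160/105 is a lesser matter of clarity.

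This rests on a literal reading of the rows and on the absence of any ranking sentence in the document. How many of the 24 patients would meet either case is unknown. The sample size, the futility and progression boundaries, and the success rule do not depend on it. No view is taken on which action is clinically right.

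**What to change.** Reconcile 7.2.6.3.2, 7.2.6.3.3, 7.2.6.3.4 and the table so that each combination of reading, earlier reduction, antihypertensive status and dose level leads to one instruction. In particular:

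- state which row governs a previously reduced patient above 150/100 but not above 160/105 who is not on maximal antihypertensives;
- state whether the hold applies above 160/105 after an earlier reduction, in the same terms in rows 2 and 3 and in the text;
- give one consistent instruction at 2 mg BID, including the restart level if there is to be a restart, across the three rows and 7.2.6.3.4;
- say whether an earlier reduction made for another toxicity counts.

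The sponsor decides which action applies in each case. The cost is a wording amendment to one table and three paragraphs, with no added visits, patients or procedures.
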